#### 4. STUDY DESIGN

This is a Phase 4, multi-center, open-label, randomized pragmatic superiority clinical trial comparing two strategies for initial or step-down oral therapy for cUTI without bacteremia with a uropathogen after 0-48 hours of parenteral antibiotic therapy. The trial will evaluate the success and safety of a strategy of initial or step-down fosfomycin, administered at a dose of 3 g once daily, vs. a strategy of initial or step-down levofloxacin administered at a dose 750 mg once daily. Initial therapy is defined as the first effective agent and step down therapy is defined as with prior effective agents. Investigator-directed adjustment to another adequate oral therapy is allowed 1) if the causative pathogen is not susceptible in vitro to quinolone initial or step-down therapy in a subject randomized to the levofloxacin strategy, *OR* 2) if the subject develops an intolerance or allergy to the initial or step-down oral therapy and at the investigator's discretion, *OR* 3) the subject has an underlying condition posing increased risk for adverse events from quinolone therapy. Another adequate oral therapy is defined as an oral therapy to which the pathogen shows in-vitro susceptibility *AND* to which the subject is tolerant based on history *AND* which is listed below:

- Levofloxacin 750 mg oral tablet once daily (Strategy 1 only)
- Fosfomycin 3 grams oral powder once daily (Strategy 2 only)
- Amoxicillin-clavulanate 875/125 mg oral tablet twice daily
- Cefixime 400 mg oral tablet once daily
- Trimethoprim-sulfamethoxazole (TMP-SMX) 160/800 mg double-strength oral tablet twice daily

The duration of oral study therapy (initial + investigator-directed adjustment if indicated) in each strategy is 5-7 days of any per protocol antibiotic to which the pathogen is susceptible such that the total duration of effective antibacterial therapy (including pre-study administration of oral therapy escalated to parenteral therapy or parenteral therapy alone) is 7 days. The dosing of oral therapy depends on creatinine clearance (CrCl) (Section 6.2).

The trial will enroll approximately 634 patients with cUTI from outpatient and inpatient settings over ~24 months. Each subject will be followed for safety and efficacy up to 28 days according to the Schedule of Study Procedures and Evaluations (Appendix A). Safety oversight will follow DMID guidelines (Section 9), and be provided by a Data and Safety Monitoring Board (DSMB)

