3.2.2. Secondary Endpoints

1. The number of solicited and unsolicited adverse events (AEs) grade 2 and above in subjects receiving fosfomycin for the duration of fosfomycin use until 2 days after last dose.
2. The number of serious adverse events (SAEs) in subjects receiving at least two doses of fosfomycin during the trial.
3. The difference in rates and severity of solicited AEs in subjects in Strategy 1 and Strategy 2.
4. The difference in the proportion of subjects achieving treatment success at EOT between Strategy 1 and Strategy 2.

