3.3. Study Definitions and Derived Variables

Clinical cure is defined as:

- Resolution of UTI symptoms from presentation (fever, hypothermia, chills or rigors or warmth, flank pain, flank tenderness, suprapubic pain, pelvic pain, suprapubic tenderness, nausea, vomiting, pain on urination, urinary frequency, urinary urgency)

AND

- No new UTI symptoms

AND

- Avoidance of parenteral antibiotic therapy, in or out of hospital, at any time after randomization **OR** oral antibiotic therapy different from per protocol

A subject will be considered a clinical failure if at least one of the above conditions is not met.

Microbiological success (Microbiologic cure) is defined as:

- Reduction of the pathogen found at presentation to $<10^4$ CFU/mL for non-catheter specimens or $<10^3$ for catheter specimens on urine culture.

Treatment success (composite cure) is defined as:

- Clinical cure and microbiological success.
- Treatment Success will be referred to as Composite Cure in manuscript TFLs.

Treatment Failure is defined as:

- A subject will be considered a treatment failure if the subject experiences clinical/microbiologic failure **OR** if the subject develops bacteremia with a uropathogen after randomization.

Adjustment-free treatment success is defined as:

- Treatment success without therapy adjustments.

Relapse infection is defined as:

- Recurrence of UTI symptoms between EOT and TOC.

End of Therapy (EOT) Visit is also referred to as Visit 3 in the protocol and will occur within 2 days of the completion of oral therapy. The window for this visit is Day 5-10 +2 days.

Test of Cure (TOC) Visit is the final visit for this study (Visit 4) and will be scheduled within the window of Day 21 + 7 days after randomization.

Day 1: is defined as the day of first dose for subjects who were treated with study product. For subjects not treated with study product, Day 1 will be defined as the day of randomization.

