4.5. Efficacy and Safety Variables

For the primary outcome, the frequency and proportion of subjects achieving treatment success at the TOC visit will be reported by treatment strategy. For the secondary and exploratory efficacy outcomes, the frequency and proportion of subjects achieving treatment success, clinical cure, microbiological success, and adjustment-free treatment success at TOC and EOT will be reported by treatment strategy and will be reported overall as well as stratified by subgroups including cUTI type, investigator-adjusted therapy, age group (<65, ≥65 years), BMI (<30, ≥30 kg/m²), sex, creatinine clearance (≥60 mL/min, <60 mL/min), indwelling urinary catheter, obstructive uropathy, diabetes, recurrent UTI status, number of days of antibiotics use (≤7, >7 days), and susceptibility to various pathogens at baseline. Note that subgroup analysis will be performed only for subgroups with total sample size above 10 subjects. Refer to Section 3.3 for definitions of treatment success, clinical cure, and microbiological success (cure).

95% confidence intervals (CIs) of frequencies of solicited and unsolicited AEs, SAEs and adverse events of special significance (AESIs) will be provided using the Wilson method.

Frequency and number of solicited AEs of grade 2 and above will be reported by treatment strategy, study day, and severity, and differences between treatment arms in frequency of grade 2 and above severity solicited AEs after the first dose of study drug will be tested using Fisher Exact Tests. For subjects receiving fosfomycin, frequency and number of each solicited adverse event of grade 2 and above severity occurring any time from date of first dose of fosfomycin in subjects receiving 2 or more doses until 2 days after last dose of fosfomycin will be tabulated. See Table 1 for schedule of study procedures.

Frequency and number of SAEs in subjects receiving at least two doses of fosfomycin during the trial will be tabulated.

All AEs will be graded for severity and relationship to study drug (see definitions below). AEs characterized as intermittent require documentation of onset and duration of each episode. The start and stop date of each reported AE will be recorded on the appropriate data collection form and eCRF.

Only Grade 2 and above AEs and SAEs will be reported. AESIs of any grade will be reported.

Severity of Event:

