9.3.1. Solicited Events and Symptoms

Solicited AEs are AEs that are common following administration of these types of antibiotics. The solicited AEs will be collected after first dose of study product is given and until the EOT. If a subject is on fosfomycin, solicited AEs will be collected for 2 days after last dose of fosfomycin or until EOT, whichever occurs later.

Solicited events were recorded for trial Days 1-12, or until study completion or termination, as the maximum severity for each day. Only grade 2 and above solicited AEs will be reported. Target solicited events include insomnia, headache, dizziness, nausea, vomiting, constipation, diarrhea, back pain, rhinitis, pharyngitis, allergic reaction, candidiasis. The solicited events were measured by grading scales as defined in Table 3.

When calculating the incidence of solicited events, each subject will be counted once at the highest severity per day, and any repetitions will be ignored. For summaries presented separately for each treatment group, the denominator will be the number of subjects who received at least one dose of the treatment with non-missing data for the event summarized.

The number and percentage of subjects reporting at least one solicited adverse event of moderate severity or higher will be summarized for each solicited symptom and any symptom in Table 38 for the Safety analysis population. For each event, the denominator is the number of subjects in the applicable treatment group who received at least one dose of study product with non-missing data for the specific event. The 95% CIs calculated using Wilson methodology from a binomial distribution (SAS Proc Freq with a binomial option) will be presented. This analysis will be repeated in Table 39 to include subjects in the Fosfomycin safety analysis population who are those who received at least two doses of Fosfomycin.

For each systemic and any systemic event, the maximum severity over 12 days after the first dose will be summarized. The number and percentage of subjects reporting each event will be summarized by the maximum severity and treatment group. For each event, the denominator is the number of subjects who received the applicable treatment with non-missing data for the specific event. The 95% CI calculated using

Wilson methodology from a binomial distribution (SAS Proc Freq with a binomial option) will be presented [Table 40](#) for the Safety population and [Table 41](#) for the Fosfomycin safety population.

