9.3.2. Unsolicited Adverse Events

The unsolicited AEs will be collected only in the Fosfomycin Safety Population which includes subjects who receive at least two doses of Fosfomycin from the time of second dose of fosfomycin until EOT or 2 days after last dose of fosfomycin whichever occurs later. The grading scale for AESIs is provided in [Table 4](#).

The number and percentage of subjects reporting at least one unsolicited AE will be summarized by MedDRA SOC and preferred term (PT). A 95% CI will be presented for the percentage of subjects reporting any unsolicited AE (serious or non-serious) for each MedDRA SOC and PT ([Table 46](#)).

The following summaries for unsolicited AEs will be presented by MedDRA SOC, PT, and treatment group:

- Incidence of AEs by severity and relationship to study product ([Table 47](#));
- Incidence of non-serious, related AEs by severity ([Table 48](#));
- Subject listing of non-serious AEs of moderate or greater severity ([Table 51](#));
- Bar chart displaying total frequency of AEs by severity, MedDRA SOC and treatment group ([Figure 5](#));
- Bar chart displaying incidence of AEs by severity, MedDRA SOC and treatment group ([Figure 6](#));

[Listing 11](#) will present details of unsolicited AEs including Subject ID, AE description, AE onset date/end date, relationship to treatment, alternate etiology if not related, outcome, and duration of event (days).

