Notes: N = Number of subjects in the Safety Population. Subjects are counted once for each category, regardless of the number of events.
AESI = Adverse Event of Special Interest.

Table 37: Number and Percentage of Adverse Events – Fosfomycin Safety Population*

[Implementation note: This table will be generated for the CSR and will be included in the paper manuscript as Table 5.]

| Adverse Event | All Subjects (N = X) | |
|---|-------------------------|---|
| | n | % |
| Any solicited adverse event grade 2 and above | x | x |
| Any unsolicited adverse event grade 2 and above | x | x |
| Any serious adverse event | x | x |
| Discontinuation of Fosfomycin in any strategy | x | x |

Notes: N = Number of Subjects who received 2 or more doses of Fosfomycin in any treatment group. Subjects are counted once for each category, regardless of the number of events.

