Note: N = Number of subjects in the Safety Population in the respective treatment group for a given symptom on the respective day(s). n = Number of subjects reporting a moderate or severe severity for a given symptom for that day.

Table 41: Number and Percentage of Subjects Experiencing Solicited Events with 95% Confidence Intervals by Symptom, Day Post Dose 1, and Treatment Group – Fosfomycin Safety Population

[Implementation note: Update footnote to use Fosfomycin Safety Population]

Table 42: Number and Percentage of Subjects Experiencing Solicited Events by Symptom, Maximum Severity, Study Day Post Dose 1, and Treatment Group - Safety Population

| Symptom | Severity | Day 1 | Day 2 | Day 3 | Day 4 | Day 5 | Day 6 | Day 7 | Days 8 | Day 9 | Day 10 | Day 11 | Day 12 | Day 13+ | Any Day |
|-------------------|-----------|---------|---------|---------|---------|---------|---------|---------|---------|---------|---------|---------|---------|---------|---------|
| | | n/N (%) | n/N (%) | n/N (%) | n/N (%) | n/N (%) | n/N (%) | n/N (%) | n/N (%) | n/N (%) | n/N (%) | n/N (%) | n/N (%) | n/N (%) | n/N (%) |
| Strategy 1 | | | | | | | | | | | | | | | |
| Insomnia | None/Mild | x/x (x) | x/x (x) | x/x (x) | x/x (x) | x/x (x) | x/x (x) | x/x (x) | x/x (x) | x/x (x) | x/x (x) | x/x (x) | x/x (x) | x/x (x) | x/x (x) |
| | Moderate | x/x (x) | x/x (x) | x/x (x) | x/x (x) | x/x (x) | x/x (x) | x/x (x) | x/x (x) | x/x (x) | x/x (x) | x/x (x) | x/x (x) | x/x (x) | x/x (x) |
| | Severe | x/x (x) | x/x (x) | x/x (x) | x/x (x) | x/x (x) | x/x (x) | x/x (x) | x/x (x) | x/x (x) | x/x (x) | x/x (x) | x/x (x) | x/x (x) | x/x (x) |
| Headache | None/Mild | x/x (x) | x/x (x) | x/x (x) | x/x (x) | x/x (x) | x/x (x) | x/x (x) | x/x (x) | x/x (x) | x/x (x) | x/x (x) | x/x (x) | x/x (x) | x/x (x) |
| | Moderate | x/x (x) | x/x (x) | x/x (x) | x/x (x) | x/x (x) | x/x (x) | x/x (x) | x/x (x) | x/x (x) | x/x (x) | x/x (x) | x/x (x) | x/x (x) | x/x (x) |
| | Severe | x/x (x) | x/x (x) | x/x (x) | x/x (x) | x/x (x) | x/x (x) | x/x (x) | x/x (x) | x/x (x) | x/x (x) | x/x (x) | x/x (x) | x/x (x) | x/x (x) |
| Dizziness | None/Mild | x/x (x) | x/x (x) | x/x (x) | x/x (x) | x/x (x) | x/x (x) | x/x (x) | x/x (x) | x/x (x) | x/x (x) | x/x (x) | x/x (x) | x/x (x) | x/x (x) |
| | Moderate | x/x (x) | x/x (x) | x/x (x) | x/x (x) | x/x (x) | x/x (x) | x/x (x) | x/x (x) | x/x (x) | x/x (x) | x/x (x) | x/x (x) | x/x (x) | x/x (x) |

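### The Fosfomycin Safety Population tables do not apply the exposure window set by the endpoint, so in subjects who changed drug they can count events from before or after fosfomycin use

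*SAP*

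**What the plan says.** **The window that is required.** Secondary endpoint 1 (Protocol 3.2.2, SAP 3.2.2) counts solicited and unsolicited AEs of grade 2 and above "in subjects receiving fosfomycin for the duration of fosfomycin use until 2 days after last dose". SAP 4.5 turns this into a tabulation rule for solicited events: those falling "from date of first dose of fosfomycin in subjects receiving 2 or more doses until 2 days after last dose of fosfomycin will be tabulated". Protocol 11.4 has the same rule for solicited events and ends unsolicited events at the same point.

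**What the analysis sections and shells do.** SAP 9.3 puts every reported AE into the summaries. SAP 9.3.1 collects solicited events from the first dose of study product until EOT or, for subjects on fosfomycin, until the later of EOT and 2 days after the last fosfomycin dose. Day 1 "is defined as the day of first dose for subjects who were treated with study product", which in Strategy 2 is normally a levofloxacin dose. For the fosfomycin tables the text is "This analysis will be repeated in Table 39 to include subjects in the Fosfomycin safety analysis population"; Tables 41, 43 and 45 are repeats of the same kind. The title of Table 41 ends "Day Post Dose 1, and Treatment Group – Fosfomycin Safety Population", Table 43 has the same time axis, and Table 45 covers the whole follow-up period. The solicited row of Table 37, "Any solicited adverse event grade 2 and above", and that of Table 34 carry no window.

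**Unsolicited events.** SAP 9.3.2 collects them "from the time of second dose of fosfomycin until EOT or 2 days after last dose of fosfomycin whichever occurs later".

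**Changing drug.** Adjustment is allowed, among other grounds, "if the subject develops an intolerance or allergy to the initial or step-down oral therapy" (Protocol 4). Fosfomycin is one of the alternatives in Strategy 2, and levofloxacin is one in Strategy 1.

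**The concern.** A Strategy 2 subject joins the Fosfomycin Safety Population only by being switched to fosfomycin and taking two doses. One permitted ground for switching is a reaction to levofloxacin. If that reaction was a solicited event of grade 2 or above, the tables as specified count it in the fosfomycin population although it preceded the first fosfomycin dose. In the other direction, a Strategy 1 subject who leaves fosfomycin after at least two doses keeps contributing events to EOT, while on the replacement drug or just after it.

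These tables answer the first secondary objective, the safety of fosfomycin. A programmer who follows SAP 9.3 and the shells will not produce the endpoint defined in SAP 3.2.2. SAP 12, which lists the changes to the planned analyses, does not mention a change of window, so this reads as an unreconciled contradiction and not as a decision.

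**Working it through.** The documents give no figure for this point, so the check compares two windows, counted in whole days from study Day 1.

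**Inputs**
- Endpoint window: first fosfomycin dose to last fosfomycin dose + 2 days (SAP 3.2.2 and 4.5).
- Tabulated window for solicited events: Day 1 to the later of EOT and last fosfomycin dose + 2 days (SAP 9.3.1).
- EOT: 0 to 2 days after oral therapy ends (Protocol 7.3, Visit 03).
- Change of drug: at the interim visit, drug Days 2 to 4. The examples given there are 2 to 4 further days after a related AE on Day 3, and 7 further days when levofloxacin non-susceptibility is found on Day 3 (Protocol 7.3, Visit 02).

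**Formulas.** Let *s* be the first fosfomycin day, *f* the last fosfomycin day and *z* the EOT day. Excess at the start = *s* − 1. Excess at the end = max(0, *z* − (*f* + 2)).

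**Solicited events**
1. *Strategy 1, no switch, 5 to 7 doses.* *s* = 1 and *z* lies between *f* and *f* + 2. Start 0, end 0. The two windows coincide (7, 8 or 9 days).
2. *Strategy 1, fosfomycin on Days 1 to 3, then k = 2 to 4 days of another drug, EOT e = 0 to 2 days later.* *f* = 3 and *z* = 3 + *k* + *e*, so the end excess = max(0, *k* + *e* − 2). With *k* = 2, *e* = 0 it is 0. With *k* = 4, *e* = 2 it is 4 (Days 6 to 9 of a 9-day window).
3. *Strategy 2, levofloxacin first, fosfomycin from s = 2, 3 or 4 for 7 days.* Start excess = 1, 2 or 3 days. The tabulated window is *s* + 8 = 10, 11 or 12 days against 9 for the endpoint. End excess is 0. A shorter fosfomycin course changes *f* but not the start excess.

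**Unsolicited events.** Collection starts at the second fosfomycin dose, so nothing from before fosfomycin can enter. The end excess is the same as in case 2.

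**Effect on a reported percentage.** If *w* Strategy 2 subjects enter the population and *r* subjects are counted only because of out-of-window events, the percentage rises by *r* / (*n*₁ + *w*), where *n*₁ is the Strategy 1 contribution. The documents give neither *w* nor *r*. Assume *n*₁ = 31 (62 enrolled, 1:1, all with two doses), *w* = 3, 6 or 9, and *r* = 1 to 3. The scale for *w* comes from 31 × 10% = 3.1 and 31 × 30% = 9.3, using the resistance range in Protocol 2.1. That range concerns non-susceptibility, not reactions, and such subjects may move to other drugs. With 6 subjects having a genuine event:

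| w | r | without extra events | with extra events | rise (points) |
|---|---|---|---|---|
| 9 | 1 | 6/40 = 15.0% | 7/40 = 17.5% | 2.5 |
| 6 | 2 | 6/37 = 16.2% | 8/37 = 21.6% | 5.4 |
| 3 | 3 | 6/34 = 17.6% | 9/34 = 26.5% | 8.8 |

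The last row needs every switcher to have reacted to levofloxacin. The table shows sensitivity and is not an estimate.

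**The case against.** The best defence is that the right window is already in the SAP: section 3.2.2 states it and section 4.5 makes it a tabulation rule, so the shells are merely silent. That is true, and it makes this a failure of carry-through and not a wrong endpoint. It does not settle the matter, because SAP 9.3 includes all reported AEs and Tables 41 and 43 are positively indexed to Dose 1.

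Second, Tables 39, 41, 43 and 45 are split by strategy, so subjects who began on levofloxacin stand in their own column, and Listings 7 and 10 show treatments and daily events. This helps for the start of the window. It does not help in Table 37, which has one pooled column and is meant for the manuscript, nor for Strategy 1 subjects switched away.

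Third, each subject is counted once, so an out-of-window event adds nothing if the subject also has an event on fosfomycin. This stands.

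A reader might infer more than the documents support:
- *That all fosfomycin AE tables are anchored on Dose 1.* Unsolicited events start at the second fosfomycin dose. That is later than the endpoint window and can lower the count.
- *That follow-up stops at EOT and the 2 days are lost.* The rule is the later of the two dates, so the 2 days are a minimum; only a cap is missing.
- *That upward bias is certain.* Fosfomycin is one of four alternatives in Strategy 2, intolerance is one of three grounds, and two doses are needed for entry.
- *That the SAE and AESI rows share the fault.* Secondary endpoint 2 counts SAEs during the trial, and AESIs are followed up to 28 days (Protocol 9.2.6).

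**Conclusion.** The point holds for subjects who changed drug. For solicited events, the tables for the Fosfomycin Safety Population exceed the endpoint window by about 1 to 3 days at the start (Strategy 2, switched to fosfomycin) and about 0 to 4 days at the end (Strategy 1, switched away). For unsolicited events only the end cap is missing. For subjects who stayed on fosfomycin the windows coincide.

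The day counts rest on a switch at the interim visit and on the protocol's own Day 3 examples; other switch days would shift them. Whether any event is misplaced is not known, because the number of switchers is not given, so any percentage is illustrative. This is a descriptive secondary endpoint in a trial stopped at 62 subjects and does not touch the primary analysis. It should be fixed, but it is not critical.

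**What to change.** State the window once in SAP 9.3 and refer to it in 9.3.1 and 9.3.2:
- In the solicited and non-serious unsolicited rows of Tables 34, 35, 37, 39, 41, 43 and 45 to 48, count an event only if its onset is on or after the first fosfomycin dose and no later than 2 days after the last fosfomycin dose. For unsolicited events the start is the second dose, when collection begins.
- Index Tables 41 and 43 to the first fosfomycin dose.
- Show events outside the window in a separate row, so that none disappears.
- Leave unchanged the SAE rows (whole trial), the AESI rows (to 28 days) and the by-strategy Safety Population tables. SAP 9.3.2 puts serious and non-serious events together in Table 46, so the filter there applies to the non-serious part only.
- Since solicited events are recorded day by day, define onset, for example as the first day reported at grade 2 or above.

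The cost is SAP wording and one derived flag from AE onset dates or daily records and fosfomycin dose dates, assuming that the product administration form cited in Listing 7 holds those dates. A few events may move out of the fosfomycin rows. One limit remains: Protocol 6.1.4 lets the old and new drug be taken on the same calendar day, and the flag cannot attribute an event on such a day.

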The trial originally planned to enroll approximately 634 subjects with cUTI from outpatient and inpatient settings over ~24 months. However, the trial was terminated in October 2019 after ~12 months of enrollment, and only 62 subjects had been enrolled. Each subject was followed for safety and efficacy up to 28 days according to the schedule of study procedures in [Table 1](#).

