4.4.3. Method of Assigning Subjects to Treatment Groups (Randomization)

Per ICH guideline E6: Good Clinical Practice, screening records will be kept at each site to document the reason why an individual was screened, but failed trial entry criteria. The reasons why individuals failed screening will be recorded in the Data Coordinating Center's (DCC's) AdvantageEDCSM (Electronic Data Capture) system.

Once consented and upon entry of demographic data and confirmation of eligibility for the trial, the subject was enrolled. Enrollment of subjects was done online using the enrollment module of AdvantageEDCSM. Subjects were randomized 1:1 to receive oral therapy from Strategy 1 or Strategy 2. Subjects were stratified by (1) pyelonephritis vs. other cUTIs and (2) participating site.

The list of randomized treatment assignments was prepared by statisticians at the DCC (The Emmes Company) and included in the enrollment module of its Internet Data Entry System (IDES). The IDES assigned each subject a treatment code and treatment assignment from the list after demographic and eligibility data had been entered.

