The proportion of subjects in each treatment group experiencing each solicited event will also be tabulated by day and severity level in [Table 42](#) for the Safety population and [Table 43](#) for the Fosfomycin safety population. Finally, solicited events will be analyzed by taking the most severe response over the follow-up period in [Table 44](#) for the Safety population and [Table 45](#) for the Fosfomycin safety population. Proportions for these derived binary variables will be reported along with 95% exact CIs. Comparisons of proportions by treatment groups will be given as odds ratio from the proportional odds model defined as:

$$\text{logit}(P(Y \leq j)) = \log\left(\frac{P(Y \leq j)}{P(Y > j)}\right) = \alpha_j + \beta \text{trt}$$
 where $j=0,1,2,3$ is the ordered severity with 0=None/Mild, 2 = Moderate, 3=Severe and $\text{trt}=1$ for strategy 1 and $\text{trt}=0$ for strategy 2. In order to interpret the model, the log of odds ratio (OR) can be expressed as

$\text{Log}[\text{odds}(\text{Severit} \leq j | \text{trt}=1) / \text{odds}(\text{Severit} \leq j | \text{trt}=0)] = \beta.$

Therefore, the odds ratio calculated as e^β can be interpreted as the odds ratio of having a maximum severity less than or equal to j for strategy 1 compared to strategy 2. The 95% CI for OR and associated p-value will be obtained from the above proportional odds model using the Wald Test.

The maximum severity occurrence of each solicited event (proportion of subjects for each severity level) will be plotted for each solicited adverse event [Figure 3](#) for the Safety population and in [Figure 4](#) for the Fosfomycin safety population. Solicited events by subject will also be presented ([Listing 10](#)).

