| | Severe | x (x) | (x, x) | x (x) | (x, x) | | |
| Pharyngitis | Moderate | x (x) | (x, x) | x (x) | (x, x) | x.x (x.x, x.x) | x.xxx |
| | Severe | x (x) | (x, x) | x (x) | (x, x) | | |
| Allergic Reaction | Moderate | x (x) | (x, x) | x (x) | (x, x) | x.x (x.x, x.x) | x.xxx |
| | Severe | x (x) | (x, x) | x (x) | (x, x) | | |
| Candidiasis | Moderate | x (x) | (x, x) | x (x) | (x, x) | x.x (x.x, x.x) | x.xxx |
| | Severe | x (x) | (x, x) | x (x) | (x, x) | | |

Note: N = Number of subjects in the Safety Population.

^a 95% CI estimated using Wilson method.

^b 95% CI for OR and P-value calculated from the proportional odds model using the Wald Test. OR can be interpreted as the odds ratio of having a maximum severity less than or equal to a severity category of *j* for strategy 1 compared to strategy 2 where *j* = 0,1,2,3.

Table 45: Number and Percentage of Subjects Experiencing Solicited Adverse Events of Moderate Severity or Greater Over the Follow-up Period by Treatment Group and Severity – Fosfomycin Safety Population

[Implementation note: Update footnote to use Fosfomycin Safety Population]

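### The Wald interval and p-value planned for solicited-event severity (SAP Tables 44–45) are invalid in any symptom row where exactly one arm has no grade 2+ event, and the SAP gives no fallback

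*SAP*

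**What the plan says.** The third secondary endpoint in SAP section 3.2.2 has two halves: "The difference in rates and severity of solicited AEs in subjects in Strategy 1 and Strategy 2".

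Rates are compared in Table 38, which gives Fisher's exact test and a Newcombe risk difference for any grade 2+ event, symptom by symptom.

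Severity is compared in Table 44 (Safety Population) and Table 45 (Fosfomycin Safety Population), using the model in section 9.3.1. Its only term is treatment, and the response "is the ordered severity with 0=None/Mild, 2 = Moderate, 3=Severe". Section 9.3.1 sets the inference: "The 95% CI for OR and associated p-value will be obtained from the above proportional odds model using the Wald Test". The Table 44 footnote repeats the method: "95% CI for OR and P-value calculated from the proportional odds model using the Wald Test". The shell has one odds ratio, interval and p-value for each symptom, plus one for any symptom. The symptoms number 12: "Target solicited events include insomnia, headache, dizziness, nausea, vomiting, constipation, diarrhea, back pain, rhinitis, pharyngitis, allergic reaction, candidiasis".

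Grade 1 is pooled with no event, in line with the reporting rule "Only grade 2 and above solicited AEs will be reported".

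The SAP has no rule for an arm without events, for non-convergence, or for penalised or exact estimation. Its minimum-size rule (sections 4.5 and 6.4) applies to efficacy subgroups only. Protocol section 11.4 names Fisher tests for solicited events and no model for severity, so the proportional-odds analysis enters with the SAP.

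**The concern.** A Wald test needs a finite estimate and a usable standard error. If every subject in one arm is in the lowest category and the other arm has at least one moderate or severe event, the likelihood keeps rising as the log odds ratio moves away from zero, and it never reaches a maximum. Software then either reports no standard error or stops at an arbitrary point with a huge one. Any p-value it prints depends on the stopping rule, not on the data.

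Arms are small and only grade 2+ events count, so such rows are plausible. At stake is a clinical study report table that could show a p-value near 1 for a symptom that Table 38 reports as significantly different between arms.

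**Working it through.** **Inputs.** Enrolment: "only 62 subjects had been enrolled" (SAP section 4.1). Allocation: "Subjects were randomized 1:1 to receive oral therapy from Strategy 1 or Strategy 2" (section 4.4.3). So n = 62/2 = 31 per arm, which is inferred; the Safety Population may be smaller. There are 12 symptoms. The plan states no figure for this comparison, so there is nothing of its own to reproduce.

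**Step 1: is there a finite estimate?** Take an illustrative row with 25 none/mild, 4 moderate and 2 severe in one arm, against 31/0/0 in the other. The profile log-likelihood at |β| = 1, 3, 5, 8 and 20 is −21.19, −19.41, −19.10, −19.053 and −19.0502. It flattens but has no maximum. As the SAP codes the model (odds of severity at or below a level, Strategy 1 against Strategy 2), the odds ratio goes to 0 if Strategy 2 is the empty arm and to infinity if Strategy 1 is. One event in the otherwise empty arm (25/4/2 against 30/1/0) restores a finite fit: |β| = 1.99, SE 1.11, p = 0.073.

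**Step 2: what would be printed?** For 25/4/2 against 31/0/0, with the response collapsed to any grade 2+ event, the Wald p-value is 0.53, 0.97 and 0.9997 after 8, 15 and 25 iterations. The three-level fit gives p = 0.82 when stopped at 20 iterations, and no standard error when run longer. Fisher's exact p for the same row is 2 × C(31,6)/C(62,6) = 0.024.

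**Step 3: how often?** Assume one grade 2+ rate p for all symptoms and both arms. The chance that a given arm is empty is q = (1 − p)^31. Exactly one arm is empty with probability 2q(1 − q), and both with probability q². Expected rows are 12 times each.

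| Rate p | q | Exactly one empty | Rows of 12 | Both empty | Rows of 12 |
|---|---|---|---|---|---|
| 2% | 0.535 | 0.498 | 6.0 | 0.286 | 3.4 |
| 5% | 0.204 | 0.325 | 3.9 | 0.042 | 0.5 |
| 9% | 0.054 | 0.102 | 1.2 | 0.003 | 0.03 |

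**Step 4: are these rates reasonable?** The nearest figures are the drug-related, all-severity rates in Protocol Tables 1 and 2. Fosfomycin has diarrhoea 9.0%, nausea 4.1%, headache 3.9% and dizziness 1.3%. The solicited symptoms listed for levofloxacin run from 1% to 7%. Use those rates symptom by symptom, with 1% assumed for fosfomycin vomiting, constipation and rash, and 1% or 5% for the other unlisted rates. The expected rows with at least one empty arm are 8.9 or 6.7, of which 3.8 or 1.7 are empty in both. That leaves 8.9 − 3.8 = 5.1 or 6.7 − 1.7 = 5.0 rows with exactly one empty arm. If half of all events are grade 2+, the corresponding results are 10.6 − 6.2 = 4.4 and 9.6 − 4.1 = 5.5.

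**Step 5: Table 45.** Its Strategy 2 column holds only subjects who took at least two fosfomycin doses, a number the documents do not give. Against 31 in Strategy 1, an assumed 2, 5 or 10 such subjects gives a 92%, 82% or 68% chance of at least one empty arm at a 5% rate, and 82%, 61% or 37% at 10%.

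**The case against.** The strongest reply is that a valid answer is already planned for these rows. When one arm lies wholly in none/mild, it has no severity split to compare, and an exact Wilcoxon test at 31 per arm gives the same p-value as Fisher's test in Table 38. Three examples against 31/0/0 confirm it: 25/4/2 gives 0.024 by both, 26/3/2 gives 0.053 and 28/2/1 gives 0.238. That stands. What is wrong is the figure Table 44 would print beside Table 38.

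Three stronger readings are tempting, and the documents do not support them:

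- **Much of the severity comparison would be blank.** Table 44 still shows counts, percentages and an interval for moderate and severe in each arm. Severity also appears in Tables 42–43, Figures 3–4 and Listing 10.
- **The clearest differences between arms would be lost.** At 31 per arm it takes 6 events against 0 to reach p ≤ 0.05, since 5 against 0 gives 0.053. Under equal rates of 2%, 5% and 9%, the expected number of rows with 6 or more against 0 is about 0.0004, 0.02 and 0.07 of 12. A large true difference could produce such a row, but Table 38 would show it.
- **The model is to blame for every row with an empty arm** (9.4, 4.4 or 1.3 of 12 at the three rates). Rows empty in both arms have a single response level, and no method can test them.

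Rates may also be higher than assumed. Nausea, vomiting and back pain overlap with the infection itself, and the phase 1 fosfomycin trial described in Protocol section 2.2 reported gastrointestinal events in over 75% of subjects, with diarrhoea mostly grade 1. At 10% or more a symptom row is usually estimable, and the any-symptom row is the least exposed.

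**Conclusion.** The point holds as a limited defect of method. The SAP prescribes a Wald interval and p-value with no fallback. In any row with exactly one empty arm, those entries are invalid and can contradict Table 38. The size is about 6.0, 3.9 or 1.2 of 12 rows at assumed rates of 2%, 5% or 9%, and about 4 to 6 rows with the protocol's own rates and the stated gap-filling. These counts rest on 31 per arm and on grade 2+ rates that the documents do not give.

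The damage is confined to the odds-ratio, interval and p-value columns of Tables 44–45. The comparison of rates and the primary endpoint are untouched. Tables 44–45 carry no asterisk, so they go to the abbreviated study report and not to the manuscript. It is worth fixing because it is cheap, not because a conclusion of the trial depends on it.

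**What to change.** In section 9.3.1 and the footnotes of Tables 44–45:

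- Replace the Wald p-value with an exact Wilcoxon, or exact trend, p-value on the three ordered levels. It matches Fisher's p in the one-empty-arm examples above, and it adds severity information when both arms have events.
- Report the odds ratio with a Firth-penalised or exact interval. Take the penalised interval from the profile likelihood. For 6 against 0 events, adding one half to each cell gives an odds ratio of (6.5 × 31.5)/(25.5 × 0.5) = 16.1 for any grade 2+ event, but a Wald-type interval around it runs from 0.86 to 299. That interval includes 1 beside an exact p of 0.024.
- Show the entry as not estimable when neither arm has an event.

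The cost is a few lines of SAP text and a standard software option, with no new data. Exact tests are slightly conservative.
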